8.10.6.2. Clinical Laboratory Data

All laboratory values will be listed. Laboratory measurements will also be summarized by treatment group and presented by time point.

8.10.6.3. ECG

All ECG values will be listed. ECG measurements will also be summarized by treatment group and presented by time point.

8.10.6.4. Vital Signs

All vital sign findings will be listed and/or summarized by treatment group.

8.10.6.5. Physical Examination

All physical examination findings will be listed and/or summarized by treatment group.

CONFIDENTIAL Page 84 of 108

9. ADVERSE EVENTS (DEFINITIONS AND REPORTING)

The Investigator is responsible for the detection and documentation of events meeting the criteria and definition of an AE or SAE, as provided in this protocol. During the study when there is a safety evaluation, the Investigator or site staff will be responsible for detecting, documenting and reporting AEs and SAEs as detailed in this Section of the protocol.

9.1. ADVERSE EVENT (AE)

An adverse event (AE) is defined as any unfavorable or unintended sign, symptom, or disease that occurs or is reported by the patient to have occurred, or a worsening of a pre-existing condition. An adverse event may or may not be related to the study treatment.

AEs will be elicited through direct questioning and subject reports. Any abnormality in physical examination findings or laboratory results that the investigator believes is clinically significant (CS) to the research subject and that occurred after initiation of the first study treatment will be reported as AEs. Abnormal findings that are NOT clinically significant should not be recorded as an AE.

9.2. REPORTING OF ADVERSE EVENTS

Report initiation for all AEs and SAEs will begin at the time of the first treatment visit and continue until the end of final study visit. All events will be followed to resolution or until the subject completes the study. A final assessment of outcome will be made at that time.

All AEs must be recorded in the subject's medical records and on the CRF. AEs will be reported using customary medical terminology along with the following information: the onset and end dates, whether the event is considered to be a SAE (see Section 9.3), the impact the event had on study treatment (see Section 9.2.1), the Common Terminology Criteria for Adverse Events (CTCAE) grade (intensity) of the event (see Section 9.2.2), the causality of the event (see Section 9.2.3), whether treatment was given as a result of the event (see Section 9.2.4), and the outcome of the event (see Section 9.2.5)

[figure not shown]
9.2.1. Impact on Study Treatment

The impact the event had on the study treatment will be assessed as either: dose increased, dose not changed, dose rate reduced, dose reduced, drug interrupted, drug withdrawn, not applicable, or unknown. The "not applicable" assessment will be used only when the subject is no longer in the Treatment Phase of the protocol.

9.2.2. CTCAE Grade (Intensity) Assessment

The guidelines outlined in CTCAE v5.0 will be used for assessing the intensity of the event (See Appendix 17.2). The general guidelines for assessing the AE grade appear below. Full guidelines may be obtained at

CONFIDENTIAL Page 85 of 108

Grade 4

Grade 5

https://ctep.cancer.gov/protocolDevelopment/electronic applications/docs/CTCAE v5 Quick Re ference 8.5x11.pdf

Grade Description Grade 1 Mild; asymptomatic or mild symptoms; clinical or diagnostic observations only; intervention not indicated. Grade 2 Moderate; minimal, local or noninvasive intervention indicated; limiting ageappropriate instrumental activities of daily living (ADL)*. Grade 3 Severe or medically significant but not immediately life-threatening; hospitalization or prolongation of hospitalization indicated; disabling; limiting self care ADL†.

Table 9-1: CTCAE v5.0 General Guidelines

Life-threatening consequences; urgent intervention indicated.

-Common Terminology Criteria for Adverse Events (CTCAE), v5.0: November 27, 2017

9.2.3. Causality Assessment

Death related to AE.

AEs will be assigned a relationship (causality) to the study treatment. The Investigator will be responsible for determining the relationship between an AE and the study treatment. The type of event, organ system affected, and timing of onset of the event will be factors in assessing the likelihood that an AE is related to the study treatment. Relationship of AEs to study treatment will be classified as follows:

- 1. Definitely related: This category applies to those AEs that the Investigator feels are incontrovertibly related to the study treatment. An AE may be assigned an attribution of definitely related if or when it meets all of the following criteria: (1) it follows a reasonable temporal sequence from administration of the study treatment; (2) it could not be reasonably explained by the known characteristics of the subject's clinical state, environmental or toxic factors, or other modes of therapy administered to the subject; (3) it follows a known response pattern to treatment with the study treatment.
- 2. Probably related: This category applies to those AEs which, after careful medical consideration at the time they are evaluated, are felt with a high degree of certainty to be related to the study treatment. An AE may be considered probable if or when (must have three): (1) it follows a reasonable temporal sequence from administration of the study treatment. (2) It could not readily have been produced by subject's clinical state, environmental or toxic factors, or other therapies administered to the subject. (3) Disappears or is decreased upon discontinuation of the study treatment. (4) It follows a known response pattern to treatment with the study treatment.

CONFIDENTIAL Page 86 of 108

^{*}Instrumental ADL refer to preparing meals, shopping for groceries or clothes, using the telephone, managing money, etc.

[†]Self care ADL refer to bathing, dressing and undressing, feeding self, using the toilet, taking medications, and not bedridden.

3. Possibly related: This category applies to those AEs which, after careful medical consideration at the time they are evaluated, are judged unlikely but cannot be ruled out with certainty to the study treatment. An AE may be considered possible if or when (must have two): (1) it follows a reasonable temporal sequence from administration of the study treatment. (2) It could not readily have been produced by subject's clinical state, environmental or toxic factors, or other therapies administered to the subject. (3) Disappears or is decreased upon discontinuation of the study treatment. (4) It follows a known response pattern to treatment with the study treatment.

- **4. Remotely related**: In general this category can be considered applicable to those AEs which, after careful medical consideration at the time they are evaluated, are judged likely to be unrelated to the study treatment. An AE may be considered unlikely if or when (must have two): (1) it does not follow a reasonable temporal sequence from administration of the study treatment. (2) It could not readily have been produced by subject's clinical state, environmental or toxic factors, or other therapies administered to the subject. (3) Disappears or is decreased upon discontinuation of the study treatment. (4) It does not follow a known response pattern to treatment with the study treatment.
- **5.** Unrelated: This category applies to those AEs which, after careful consideration at the time they are evaluated, are clearly and incontrovertibly due to extraneous causes (disease, environment, etc.) and determined with certainty to have no relationship to the study treatment.

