Current human experience with leronlimab (PRO 140) consists of nine completed and six ongoing clinical trials, mostly on healthy subjects or HIV-1 positive subjects. These studies are summarized in Table 1-1 and Table 1-2. In all clinical trials, the majority of adverse events (AEs) have been mild or moderate. No dose-limiting toxicities or patterns of drug-related toxicities were observed. Antiviral activity was potent, rapid, prolonged, dose-dependent, and highly significant.

CONFIDENTIAL Page 25 of 108

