1.6. RISKS / BENEFITS ASSESSMENT

Allergic Reaction

Leronlimab (PRO 140) belongs to the monoclonal antibody class of drugs. Monoclonal antibodies are sometimes associated with allergic reactions or flu-like reactions (such as fever, chills, and aches) or injection-site reactions. These events are usually of short duration if they occur at all. Severe allergic reactions, however, can be life-threatening. Although anaphylaxis has not been observed in prior trials of leronlimab (PRO 140), the protein infusion always carries theoretical risk for anaphylactic shock. Accordingly, whenever leronlimab (PRO 140) is administered to subjects, procedures should be available and in place to manage the occurrence of anaphylactic shock.

Immune Response

People who take leronlimab (PRO 140) or other monoclonal antibodies can also develop an immune response to leronlimab (PRO 140) that may affect their ability to receive monoclonal antibodies, or to benefit from diagnosis or therapy with a monoclonal antibody in the future.

Pregnancy

Risks to unborn babies exposed to leronlimab (PRO 140) are unknown at this time; thus pregnant females will be excluded from this study. Females of childbearing potential must have a negative pregnancy test prior to enrollment. Both male and female patients and their partners of childbearing potential must agree to use appropriate birth control methods throughout the study duration (excluding women who are not of childbearing potential and men who have been sterilized).

Venipuncture

Blood sampling is required as part of the study protocol. Blood sampling carries a minimal risk of minor discomfort and the possibility of minor bruising at the site of the needle puncture and, rarely, the possibility of infection at the needle puncture site.

Unknown Risks

As with all research, there is the remote possibility of risks that are unknown or that cannot be foreseen based on current information.

CONFIDENTIAL Page 41 of 108

[figure not shown]

Theoretical risk for increased severity of West Nile virus infection

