5.2. EARLY STOPPING RULES

Upon occurrence of any of the following events, data will be reviewed by the Medical Monitor and the Lead Principal Investigator.

- 1. Death in any subject in which the cause of death is judged to be probably or definitely related to the study drug by the treating investigator;
- 2. The occurrence in any subject of a life-threatening SAE whose causal relationship to study drug is judged to be probable or definite by the treating investigator;
- 3. Two (2) occurrences of Grade 4 toxicities that are assessed to be probably or definitely related to the study drug by the treating investigator;
- 4. Two (2) occurrences of a Grade 2 or higher allergic/hypersensitivity reaction directly related to the study drug that lead to permanent discontinuation of study drug.

In case the above listed event(s) occurred, patient accrual will be suspended pending further review and the FDA and other global regulatory authority will be notified. The study will be stopped if any of these stopping criteria are met unless, after reviewing the safety events of interest, the medical monitor and Sponsor, agree to allow the study to proceed. The FDA and other global regulatory authority will be consulted for any protocol amendment before restarting the trial if a stopping rule is met.

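### Under the causality checklist, a fatal reaction of a type not seen before with leronlimab scores at most two of four criteria, so as written it cannot be rated 'probably related' and does not meet the Section 5.2 death rule

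*Protocol*

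**What the plan says.** Protocol Section 5.2 lists events that suspend accrual and lead to notification of regulators. The first is "Death in any subject in which the cause of death is judged to be probably or definitely related to the study drug", as judged by the treating investigator. A death rated *possibly related* is not on the list.

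Protocol Section 9.2.3 defines the classes:

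- *Definitely related*: "An AE may be assigned an attribution of definitely related if or when it meets all of the following criteria". The three criteria are timing, no other reasonable explanation, and that "it follows a known response pattern to treatment with the study treatment".
- *Probably related*: described as a class for events that the investigator firmly believes are due to the treatment, and then: "An AE may be considered probable if or when (must have three". The four criteria are (1) timing, (2) not readily produced by clinical state or other therapy, (3) "Disappears or is decreased upon discontinuation of the study treatment", and (4) a known response pattern.
- *Possibly related*: described as a class for events thought improbable but not excludable, and then: "An AE may be considered possible if or when (must have two", from the same four criteria.

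On what is known of the drug, Section 1.4.2 says: "No dose-limiting toxicities or patterns of drug-related toxicities were observed". Section 1.5.2 reports that the definitely related events at 700 mg in the earlier HIV study were all mild or moderate injection site reactions. Section 1.6 says: "Although anaphylaxis has not been observed in prior trials of leronlimab (PRO 140".

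**The concern.** Two of the four criteria depend on features that a first, unexpected, drug-caused death cannot have. Resolution after stopping is impossible once the subject has died. A known pattern is impossible if the reaction has not been seen with this drug. On the protocol's own account no serious or fatal response pattern has been observed with leronlimab, so a drug-caused death could well be of a new type.

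At stake is whether a death that the investigator attributes to the drug with confidence leads to the suspension and notification in Section 5.2. The same checklist would move that event out of the *probably* row of the by-causality TEAE table (SAP Section 9.3.1). An investigator in this position has two instructions in one paragraph that point to different classes.

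**Working it through.** The plan gives no figure to reproduce. The check is an enumeration of the decision rule.

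**Inputs** (Protocol 9.2.3). Let c1 to c4 be 1 if the criterion is met and 0 if not. Criterion (2) is worded slightly differently for *definitely* and *probably*; the enumeration treats it as one item.

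- *Definitely*: c1 = c2 = c4 = 1
- *Probably*: c1 + c2 + c3 + c4 ≥ 3
- *Possibly*: c1 + c2 + c3 + c4 ≥ 2

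**All combinations.** There are 2^4 = 16. Those with a sum of at least 3 number 4 (exactly three met) + 1 (all met) = 5. The two that satisfy *definitely* are already among these five. Each of the five has c3 = 1 or c4 = 1, because c1 and c2 alone give only 2.

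**Fatal event of a new type.** Set c3 = 0 and c4 = 0. The maximum is 1 + 1 + 0 + 0 = 2, which is below 3, and *definitely* fails because c4 = 0. Of the 2^2 = 4 remaining combinations, 0 reach either class.

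**Best case by type of event:**

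| Event | (1) | (2) | (3) | (4) | Met | Highest class | Section 5.2 |
|---|---|---|---|---|---|---|---|
| Fatal, known pattern | yes | yes | no | yes | 3 | *definitely* | rule 1 met |
| Fatal, new type | yes | yes | no | no | 2 | *possibly* | rule 1 not met |
| Life-threatening, new type, resolves on stopping | yes | yes | yes | no | 3 | *probably* | rule 2 met |

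**Events after the last dose.** Table 6-1 gives two weekly doses, at Day 0 and Day 7, and adverse events are collected to the last visit at Day 42. For 42 − 7 = 35 days there is no further dose to discontinue, so criterion (3) cannot strictly be assessed for non-fatal events either. An investigator might credit fading after the last dose as meeting it; the text does not say.

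**Other rules in 5.2.** Rules 2 and 3 use the same probable-or-definite threshold. Rule 4 needs two hypersensitivity reactions, so a single fatal one does not meet it. Section 5.3, by contrast, counts *possibly related* events as attributable when deciding whom to follow to resolution.

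**The case against.** The strongest reply is that rule 1 depends on the treating investigator's judgement, and 9.2.3 introduces its criteria permissively. An investigator who is confident that the drug caused the death satisfies the description of *probably related* and would hardly choose a class for improbable events. This has force: the documents contain a conflict between a description and a checklist, not a disabled rule. But the count of three is mandatory on its face, and a site that follows it will under-classify the event.

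The safeguards are also real. SAEs go to the Medical Monitor within 24 hours (Protocol 9.4). The DSMC receives deaths and may recommend stopping at any time (SAP 5.1.5 and 5.1.6), and it may convene when it chooses (Protocol Section 12). These limit the harm, but neither carries the automatic suspension and notification of Section 5.2, and the scheduled looks are only at about 25%, 50% and 75%.

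A reader might infer more than the documents support:

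- *That the death rule can never be met.* It can, for a fatal event with a known pattern.
- *That fatal anaphylaxis certainly escapes it.* This is arguable. Section 1.6 treats severe allergic reaction as a risk of the antibody class, and Section 9.6 leaves expected events to the Investigator Brochure, which is not among the documents. An investigator could regard the pattern as known, although 9.2.3 ties it to the study treatment.
- *That 'probably' merges with 'definitely' for fatal events.* The wording of criterion (2) and the required level of confidence both differ between the classes.
- *That the planned number of deaths measures the gap.* The planning rates imply 0.30 × 260 + 0.45 × 130 = 78 + 58.5 = 136.5 deaths. Most of these could be explained by COVID-19 and would fail criterion (2) under any checklist. The figure shows how often causality must be judged, not how often it would be wrong.

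**Conclusion.** The point stands, with moderate importance. If the checklist is followed as written, a fatal reaction of a type not seen before with leronlimab scores at most 2 of 4, is rated *possibly related*, and does not meet rule 1 of Section 5.2, however confident the investigator is. This rests on two readings: that the required count of three binds, and that a known pattern means one known for leronlimab.

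The number of events that would fall in the gap cannot be estimated from the documents. The effect on the TEAE tables is limited, because all five classes are tabulated beside overall and SAE summaries and no safety inference is planned. Protocol Section 8.3 adds the open-label phase after randomized enrollment is complete; from that stage a suspension of accrual would bear mainly on that phase (about 100 subjects).

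**What to change.** Reconcile 9.2.3 with 5.2.

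- In 9.2.3, state that a criterion that cannot be assessed does not count against *probably related*. Name the cases: criterion (3) when the event is fatal or follows the last dose, and criterion (4) when the event type has not been reported before with leronlimab.
- Keep three of four where all four can be assessed. One exact wording is to require three criteria, or all assessable criteria if fewer than three can be assessed. A fatal new-type event then needs both (1) and (2); with three or four assessable criteria the threshold stays at three.
- Leave *definitely related* unchanged, so that a new-type event cannot reach it on two criteria.
- Have 5.2 refer to this classification.

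A rule that simply demands every assessable criterion should be avoided, because it would tighten ordinary cases from 3 of 4 to 4 of 4.

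The cost is a wording amendment and a memo to sites. The downside is that a few more events may be rated *probably related* and prompt a review.

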8.2.4. Safety Measures

Safety will be assessed using:

- Incidence of treatment-related adverse events (TEAEs)
- Incidence and severity of treatment-emergent adverse events (TEAEs)
- Incidence of serious adverse events (SAEs)
- Incidence of TEAEs and SAEs leading to discontinuation of study medication.
- Changes in blood chemistry, hematology and coagulation parameter results
- Changes in vital signs including temperature, pulse, respiratory rate, systolic and diastolic blood pressure
- Changes in physical examination results
- Changes in electrocardiogram (ECG) results

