#### 9.3.1 Adverse Events

Adverse events will be coded using the most recent version of Medical Dictionary for Regulatory Activities (MedDRA). Treatment Emergent AE's (TEAE) are defined as events with an onset on or after the first treatment. TEAEs will be summarized by System Organ Class and preferred term by treatment group. The following TEAE summaries will be provided:

- Overall (i.e., regardless of severity or relationship to treatment);
- By intensity (mild, moderate, severe, life threatening or death);
- By causality (definitely, probably, possibly, remotely or unrelated);
- By impact on study treatment (dose increased, dose not changed, dose rate reduced, dose reduced, drug interrupted, drug withdrawn, not applicable, or unknown).

In addition, separate summaries of serious adverse events, and adverse events resulting in discontinuation of study treatment will be presented.

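### Two of the four 'Remotely related' criteria point toward causation, so by the checklists an adverse event can qualify as both probably and remotely related

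*Protocol*

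**What the plan says.** Protocol 9.2.3 makes the investigator responsible for causality and defines five categories. Four of them combine an opening judgement with a checklist.

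- *Definitely*: "An AE may be assigned an attribution of definitely related if or when it meets all of the following criteria". The three criteria are timing, no other reasonable explanation and a known response pattern.
- *Probably*: events that "are felt with a high degree of certainty to be related to the study treatment". The rule reads: "An AE may be considered probable if or when (must have three): (1) it follows a reasonable temporal sequence from administration of the study treatment". The other criteria are no ready alternative explanation, abatement on stopping the drug and a known response pattern.
- *Possibly*: the same four criteria with a lower threshold: "An AE may be considered possible if or when (must have two): (1) it follows a reasonable temporal sequence".
- *Remotely*: events that "are judged likely to be unrelated to the study treatment", with two of four criteria required. The timing criterion is reversed. The alternative-explanation criterion is not. The list ends "3) Disappears or is decreased upon discontinuation of the study treatment. (4) It does not follow a known response pattern", so abatement on stopping is not reversed and response pattern is.

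*Unrelated* has no checklist and requires certainty that the cause lies elsewhere.

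The ratings are used in several places. Protocol 8.2.4 and SAP 3.4 list "Incidence of treatment-related adverse events (TEAEs" as a safety measure. SAP 9.3.1 tabulates treatment-emergent events "By causality (definitely, probably, possibly, remotely or unrelated". Protocol 5.2 has four events that suspend accrual, and three of them depend on a probable or definite rating. Protocol 5.3 groups definite, probable and possible events as attributable when it requires follow-up of events still ongoing at the last visit. The SAP gives no causality definitions of its own, and neither document says which categories make up the treatment-related measure.

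**The concern.** An event with no other ready explanation that abates when the drug is stopped is one an investigator would normally regard as suggestive of a drug effect. As written, those two features alone satisfy the checklist for the category next to unrelated. A rater who follows the checklist rather than the opening judgement could file such an event as remote. It would then leave any grouping of definite, probable and possible events, and it would not count toward the three stopping triggers that need a probable or definite rating.

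The matter is more acute in the open-label phase, where ratings are made with knowledge of treatment and the subjects join the Safety population (SAP 7.4).

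**Working it through.** The plan states no figure here, so there is nothing to reproduce. The check is a full enumeration of the criteria.

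**Inputs (all from Protocol 9.2.3).** Score each criterion 1 if true and 0 if not: T = reasonable timing, N = not readily explained otherwise, D = abates on discontinuation, K = known response pattern. Four yes/no criteria give 2⁴ = 16 patterns.

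**Rules**, reading the required number as a minimum:

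- Definite: T = N = K = 1
- Probable: T + N + D + K ≥ 3
- Possible: T + N + D + K ≥ 2
- Remote as written: (1−T) + N + D + (1−K) ≥ 2
- Remote with (2) and (3) reversed: (1−T) + (1−N) + (1−D) + (1−K) ≥ 2, that is, T + N + D + K ≤ 2

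**The five Probable patterns**

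| True criteria | Remote score as written | Meets Remote? | Remote score after reversal | Meets Remote? |
|---|---|---|---|---|
| T, N, D, K | 0+1+1+0 = 2 | yes | 0 | no |
| T, N, D | 0+1+1+1 = 3 | yes | 1 | no |
| T, N, K | 0+1+0+0 = 1 | no | 1 | no |
| T, D, K | 0+0+1+0 = 1 | no | 1 | no |
| N, D, K | 1+1+1+0 = 3 | yes | 1 | no |

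So 3 of 5 overlap as written and 0 of 5 after reversal. Two of these patterns also meet Definite (T, N, D, K and T, N, K). One of the two meets Remote as written and neither does after reversal. The pattern with all four criteria true meets Definite, Probable, Possible and Remote at once.

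**Possible against Remote.** Possible covers 6 two-criterion patterns plus the 5 above, 11 in all. As written, the two-criterion Remote scores are TN 2, TD 2, TK 0, ND 4, NK 2 and DK 2, so 5 of 6 overlap. Adding the 3 above gives 8 of 11. After reversal, all 6 two-criterion patterns overlap and none of the other 5 do, giving 6 of 11. Five of the present 8 overlaps therefore persist, and TK becomes a sixth. That remainder is structural: both categories accept two of four.

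**Gap at the other end.** As written, T alone scores 0+0+0+1 = 1 for Remote and K alone scores 1+0+0+0 = 1. Both also fall short of Possible, so these patterns meet neither checklist. After reversal, every pattern meets Possible or Remote.

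**Sensitivity to the reading of the threshold.** If the required numbers meant exactly three and exactly two, the four three-criterion patterns would have Remote scores of 3, 1, 1 and 3, and none would overlap. But an event with all four criteria would then fail Probable while still meeting both Definite and Remote (score 2). That reading does not rescue the text.

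**The case against.** The strongest reply is that the checklists do not govern. Causality is the investigator's determination, each category opens with an overall judgement, and the checklists say only that an event may be so classed. High certainty of a relationship and likely absence of one exclude each other, so an investigator convinced of a drug effect is not directed to *Remotely*. This stands for *Probably* against *Remotely* and limits the harm. It is weaker for *Possibly* against *Remotely*, because the *Possibly* opening and the *Remotely* checklist both use the word unlikely.

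All three *Probably*/*Remotely* overlaps also need N and D together. Subjects are severely ill, many co-therapies are allowed, and only two doses are given, after which nothing remains to discontinue. The combination is plausibly uncommon, though the documents give no frequencies.

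A reader might infer three stronger conclusions that the documents do not support.

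- *The treatment-related count is corrupted.* No event is recorded in two categories, no misfiled event is shown, and the composition of the count is undefined. The five categories are tabulated separately, the overall and serious-event summaries ignore causality, and the Protocol synopsis plans no inferential safety statistics. Randomized-phase rating is blinded (Protocol 8.6), so misfiling need not favour an arm.
- *Remote events lose follow-up.* Protocol 9.2 follows all events to resolution or study completion, and 9.5 follows all serious events until they stabilize, whatever the cause. The loss is limited to non-serious events still ongoing at the final visit.
- *The 8 of 11 Possible/Remote overlap measures the harm of the copying error.* Six of 11 overlap even after correction. The patterns are also abstract and equally weighted; they are not event frequencies.

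**Conclusion.** The definition is wrong as written. Two of its four criteria point the opposite way from the category they define, and 3 of the 5 patterns that qualify as *Probably* also qualify as *Remotely*. The categories are ambiguous, the treatment-related tabulation in Protocol 8.2.4 and SAP 9.3.1 is unreliable to that extent, and the ratings used by three of the four stopping triggers can be affected.

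The conclusion rests on reading the required numbers as minimums. It applies to the checklists, and it becomes a misclassification only where a rater follows the checklist over the opening judgement. How often that would happen, and hence the size of any miscount, cannot be derived from the documents.

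**What to change.** 1. In *Remotely related*, reverse criterion (2) so that it says the event could readily be explained by the subject's condition, surroundings or other treatment. Reverse criterion (3) so that it says the event does not abate when study treatment stops. This brings the *Probably*/*Remotely* overlap from 3 of 5 to 0 of 5 and closes the gap for T alone and K alone.
2. Send sites a short clarification.
3. State in the SAP which categories count as treatment-related. The only existing grouping is the one in Protocol 5.3, written for follow-up.

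Two further steps are optional. A tie-break rule would settle the 6 two-criterion patterns that still meet both *Possibly* and *Remotely*, but those come from the thresholds rather than from the copied criteria. Events already rated *Remotely related* could be reviewed; for the randomized phase this should be done blinded and before database lock, because it replaces ratings made at the time with retrospective ones.

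The cost is two wording changes in the protocol, a site memo and a sentence in the SAP, plus a limited query if the review is done.
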